4.0 Patient Selection and Withdrawal

A total of 120 male patients who have advanced androgen-sensitive advanced prostate cancer will be enrolled in this study. Patients providing written informed consent and who meet the following inclusion/exclusion criteria will be eligible.

4.1 Inclusion Criteria

1. Males, Ages 18 and older
2. Body Mass Index (BMI) between 18 and 35 kg/m² (inclusive)
3. Not currently hospitalized
4. Clinical indication of adenocarcinoma of the prostate evidenced by a biopsy report on record
5. At present receiving ADT treatment with
 - a. a GnRH agonist
 - b. for at least 2 months but not longer than 36 months without interruption

Note: If the patient received GnRH agonist treatment prior to the treatment described under 5a and b, there must be evidence of a period without GnRH agonist treatment for a minimum of 2 months prior to starting the present treatment as is seen, for example with intermittent treatment regimens.

6. Able to initiate Screening procedures 2 weeks prior to the next scheduled injection with a GnRH agonist
7. Willing to discontinue current ADT regimen for the duration of the study
8. T level less than 50 ng/dL at Screening
9. WHO/ECOG performance status of 0 or 1
10. Life expectancy of at least 1 year
11. Adequate renal function demonstrated by not having elevated blood urea nitrogen (BUN) or Creatinine Screening lab values
12. Willing and able to communicate with the Investigator and study staff, and willing and able to complete all phases and all procedures required of the study
13. Provide voluntarily consent to participate in this study and provide written informed consent prior to start of any study-specific procedures

4.2 Exclusion Criteria

1. History or presence of allergic or adverse response to estradiol
2. Presence of symptomatic metastatic disease, risk of spinal cord compression or presence of clinically significant urinary obstruction as determined by the Principal Investigator

3. History within the past 2 years of deep vein thrombosis (DVT), pulmonary embolism (PE₂), a known thrombophilic disorder (eg.protein C, protein S, or antithrombin deficiency), or cerebrovascular accident (CVA)
4. History within the past 2 years of myocardial infarction or a coronary vascular procedure (e.g. percutaneous coronary intervention, coronary artery bypass graft)
5. History of congestive heart failure
6. Use of any investigational drug, biologic, or device within 28 days prior to the first dose of study drug
7. Use of any of the following known inducers or inhibitors of cytochrome P450 3A4 (CYP3A4): phenobarbital, carbamazepine, rifampin, erythromycin, clarithromycin, ketoconazole, itraconazole, ritonavir, St. John's Wort preparations (*Hypericum perforatum*), and grapefruit juice
8. Hematological parameters (Hematocrit or Hemoglobin) outside 20% of the upper or lower limits of normal at Screening
9. Active skin rash, sunburn, or other skin disorder on the upper arm(s) that requires treatment or may affect skin absorption of study gel
10. Resting uncontrolled hypertension (HTN) (160/100 mmHg) at Screening
11. Co-existent malignancy or a history of malignancy during the past 5 years, with the exception of basal and/or squamous cell carcinoma of the skin
12. Any other significant concurrent illness or disease or condition that in the opinion of the Investigator might interfere with the patient's ability to receive the treatment outlined in the protocol or might put him at additional risk

4.3 Early Withdrawal of Patients

A patient is free to withdraw from the study at any time for any reason without prejudice to their future medical care by the physician or at the institution. The Investigator or Sponsor may also withdraw the patient at any time in the interest of patient safety. The primary reason for withdrawal must be recorded in the patient's medical record and on the withdrawal form in the Case Report Form (CRF). If a patient is withdrawn for more than one reason, each reason should be documented in the source document and the most medically significant reason should be entered on the CRF. The withdrawal of a patient from the study should be discussed where possible with the Medical Monitor before the patient stops administration of the study drug. If the study drug is discontinued, the final evaluations will be performed as completely as possible. Any comments (spontaneous or elicited) or complaints made by the patient and the reason for termination, date of stopping study drug and the total amount of study drug administered must be recorded in the CRF and source documents.

The following are reasons to terminate the participation of a patient in the study:

- The patient is no longer chemically castrated, after 4 weeks of double-blind treatment or anytime thereafter, indicated by a measurement of T \geq 50 ng/dL. (*treatment failure*)
- The patient's PSA rises >0.5 ng/mL above the baseline measurement (*treatment failure*)
- Lost to follow-up: patient fails to return to the study site for scheduled visits and does not respond to multiple telephone or written attempts to contact (these attempts should be documented).
- Withdrawal of consent: patient decides to stop participation in the study for any reason or is unable to complete the study as described in the study protocol. Although a patient is not obliged to give his/her reason for withdrawing prematurely, the Investigator will make a reasonable effort to obtain the reason while fully respecting the patient's rights. Every effort will be made to contact a patient who fails to attend any follow-up appointments/contacts in order to complete study assessments.
- Administrative: the Sponsor decides to terminate or discontinue the study (either at the study site or the entire study).

4.4 Patient Replacement

Randomized patients who do not complete the study for any reason will not be replaced.

5.0 Study Drug

Study drug will only be shipped to Investigators who have provided BHR PHARMA, LLC (or an authorized representative) all required study documents, including Institutional Review Board (IRB) approval, have executed a clinical trial agreement (CTA), and have been approved by BHR PHARMA, LLC to begin the study. Study drug will be provided by BHR PHARMA, LLC (or authorized representative) as blind-labeled ready-to-use canisters containing BHR-200 (0.36% transdermal estradiol gel) or placebo.

5.1 Blinding and Unblinding

All site personnel will be blinded to treatment assignment. The Investigator (or designee) will be responsible for drug accountability and dispensing of the study drug.

In the case of an AE or serious adverse event (SAE) for which the Investigator must know a specific treatment allocation to ensure the patient's safety, unblinding of treatment assignment is permitted. Instructions for "breaking the blind" will be provided to the Investigator. It should be stressed that unblinding the treatment allocation is only allowed for safety concerns in an emergency situation. If time allows, the Investigator is encouraged to discuss the matter with the study Medical Monitor prior to "breaking the blind" whenever possible.

If possible, the relationship of the AE to the study drug should be assessed before the treatment code is broken. In all cases, the Medical Monitor must be notified within 24 hours after the code has been broken.

If the treatment assignment is unblinded, study drug may be discontinued at the Investigator's discretion.

5.2 Formulation, Packaging, and Labeling

The BHR-200 drug product consists of [REDACTED]
[REDACTED]
[REDACTED]
[REDACTED]

The placebo drug product is an absorptive hydro-alcoholic gel preparation of the same ingredients as BHR-200, but without 17 β -estradiol.

Both drug products are provided in ready-to-use, plastic canisters with a metered-dose pump capable of delivering 1 milliliter of gel, and labeled 'For Investigational Use Only'. A resealable polypropylene cap tops the canister to protect the pump. Each individually packaged canister is capable of delivering at least 90, 1mL metered doses of gel.

5.3 Storage

All study drug must be stored in a secure limited-access area, at controlled room temperature (20 – 25° C [68° to 77°F]); excursions are permitted to 15° to 30°C [59° to 86°F]) in accordance with labeled storage requirements. Patients will be instructed to store the study drug at home at room temperature, and to avoid extreme heat or cold during transportation from the clinic to home. Patients will be provided with an insulated bag to be used when transporting the study drug from the clinic to the patient's home. Investigational labeling will include instructions to keep the product out of the reach of children.

5.4 Dispensing

The Investigator (or designee) will only dispense the specific numbered canisters of the study drug as allocated by central pharmacy to the patient. Two (2) canisters will be dispensed at a time.

5.5 Dosage and Administration

Patients will self-apply either BHR-200 or placebo as a metered unit dose (one actuation or multiples thereof, [Table 2](#)) of gel daily to clean, dry, intact skin of the upper arms and shoulders as shown in the shaded areas in [Figure 2](#). The gel should not be applied to any

other parts of the body, including the abdomen or genitals. The area of application should be limited to the area that would be covered by a short sleeve t-shirt. It is advised to apply study drug in the morning after showering. Night-time application is acceptable, but caution should be taken to limit transfer to other individuals. Application should occur approximately at the same time daily. A patient study drug administration guideline is provided in [Appendix 2](#).

When a canister is used for the first time, it must be primed. To prime the canister, remove the cap from the canister and push the pump all the way down until gel is dispensed. Complete the priming process by pushing the pump all the way down an additional three (3) times. Do not use any gel that came out while priming. Discard the gel by washing it down the sink to avoid accidental exposure to others. It is only necessary to prime the pump before the first dose is dispensed. (Repeat priming each time a new canister is opened.) After priming, the canister is ready to use. One complete press of the pump will deliver approximately the same amount of gel each time. The Investigator (or designee) will prime the study drug canister(s) prior to dispensing to the patient.

Table 2
Study Drug Dose and Application Sites

Total Number of Pump Actuations*	Pump Actuations Per Upper Arm and Shoulder	
	Upper Arm and Shoulder: #1	Upper Arm and Shoulder: #2
1 actuation	1	0
2 actuations	1	1
3 actuations	2	1

*1 actuation of the pump dispenses [REDACTED]

Figure 2
Application Sites for BHR-200 and Placebo gel

5.6 Study Drug Administration Precautions

- Only the patient should apply the study drug. Others (study staff and/or patient’s family members) should not apply the study drug to the patient.

- The patient should not make contact with the area of skin where the study drug was applied for at least 1 hour after the application.

If someone else is exposed to the study drug by direct contact with the study drug, that person should wash the area of contact with soap and water as soon as possible. The longer the study drug is in contact with the skin the greater the chance that the other person will absorb some of the estrogen hormone. **This is especially important for children.**

No skin-to-skin transfer studies with BHR-200 (estradiol gel) have been conducted. However, a study conducted in women with a similar FDA-approved product, EstroGel® (0.06% estradiol gel), showed that skin-to-skin contact between treated and non-treated women 1 hour after application of the gel, neither resulted in a statistically significant or clinically important transfer of estradiol gel to the non-treated women nor was there subsequent absorption of estradiol by the non-treated women (ZumBrunnen et al. 2006). Use of lotions and creams on the application site is not allowed. Use of sunscreen products is allowed 1 hour after application. Although no studies have been performed with BHR-200, a study with repeated daily application of sunscreen for 7 days at 1 hour after the administration of EstroGel® (0.06% estradiol gel) decreased the mean AUC and Cmax of estradiol by not more than 16% (EstroGel® Package Insert Rev. 08/2014).

5.7 Assessment of Compliance

Study drug compliance will be performed at each study visit. If the study drug is discontinued or interrupted, the reason(s) will be recorded.

Study drug canisters will be weighed after priming of the canister and when the canister is returned. The canister weight(s) will be recorded in grams.

5.8 Drug Accountability

The Investigator will maintain accurate records of the disposition of all clinical drug supplies received during the study and the dates on which drug supplies were received from BHR PHARMA, LLC or authorized representative. At the conclusion of the study, any unused study gel will be destroyed by the site upon written authorization by BHR PHARMA, LLC and pursuant to applicable federal and state regulations or returned to BHR PHARMA, LLC or their designee.

5.9 Prior and Concomitant Medications

All medications, on-going and new, administered or taken by the patient during the study (from time of consent through Week 24) are to be recorded on the CRF. Information should

be recorded for: name of drug, dose, route of administration, start and end dates and time (for i.v. drugs), and indication.

Any therapeutic or surgical procedure performed for concurrent conditions through Study Week 24 should be recorded, including the date, description of the procedure, and clinical findings.

5.10 Prohibited Concomitant Medications/Therapies

Investigational drugs or therapies should not be used at any time during the study because of their potential to confound the results. The following interventions are prohibited during the study because of their potential to confound the results:

- Administration of any of the following prostate cancer treatments:
 - Immunotherapy (e.g., antibody therapies, tumor-vaccines)
 - External radiotherapy
 - Brachytherapy
 - Chemotherapy
 - Biological response modifiers (e.g., cytokines)
 - GnRH agonists (e.g. Lupron[®], Eligard[®], Viadur[®], Vantas[®], Trelstar[®], Zoladex[®])
 - GnRH antagonists (e.g. Firmagon[®])
 - Antiandrogens (e.g. Casodex[®], Eulexin[®], Nilandron[®])
 - Androgen inhibitors (e.g. Zytiga[®], Xtandi[®])
- Any of the following prostatic or other related surgery :
 - Transurethral resection of the prostate
 - Radical prostatectomy
 - Orchiectomy
 - Adrenalectomy
 - Hypophysectomy
- Application of prescription or over-the-counter (OTC) topical products (including but not limited to: gel, patch, cream, ointment, lotion, or spray) to the study drug application site(s), i.e. on the upper arm(s) and shoulder(s). An exceptions is the use of sunscreen products > 1 hour after application of the study drug.
- Prescription or OTC treatments that are known/suggested to have an estrogenic or anti-androgenic effect.
- Any of the following known inducers or inhibitors of cytochrome P450 3A4 (CYP3A4): phenobarbital, carbamazepine, rifampin, erythromycin, clarithromycin,

ketoconazole, itraconazole, ritonavir, St. John's Wort preparations (*Hypericum perforatum*), and grapefruit juice.

6.0 Study Evaluations

6.1 Laboratory Tests

Laboratory tests will be performed by a central laboratory. The following test results will be reported to the Investigator: hematology, blood chemistry, urinalysis, coagulation factors, hormones (including total Testosterone), and PSA. The Investigator will assess all abnormal lab values for clinical significance; if categorized as adverse events, they will be collected and recorded similarly to other AEs. All clinically significant abnormal lab values will be followed until resolution. If resolution is not seen, a justification as to the cause for such an abnormality, such as due to an underlying pre-existing condition, associated co-morbidity, etc., will be recorded.

The following laboratory assessments will be performed for this study.

Hematology:	Hematocrit, Hemoglobin, WBC with differential, RBC, Platelets
Blood Chemistry:	Alanine transaminase (ALT), Albumin, Alkaline phosphatase (ALP), Aspartate aminotransferase (AST), Blood urea nitrogen (BUN), Calcium, Carbon dioxide, Chloride, total Cholesterol, Cholesterol HDL, Cholesterol LDL, Creatinine, Direct bilirubin, Glucose, Lactate dehydrogenase (LDH), Potassium, Sodium, total Bilirubin, total Protein, Triglycerides
Coagulation Factors:	Protein C-activity and antigen, Protein S-activity, Protein S-antigen, Antithrombin III antigen, and Activated protein C resistance (APCR)
Endocrine:	Glycated hemoglobin (HbA1C)
Hormones:	Follicle stimulating hormone (FSH), Luteinizing hormone (LH), and Sex hormone-binding globulin (SHBG)
Urinalysis:	Appearance, Color, Glucose, Ketones, Microscopic, Nitrites, Occult blood, pH, Protein, Specific Gravity
Biomarkers:	
Bone:	C-telopeptide crosslink of type 1 collagen (CTX) – bone resorption

Alkaline Phosphatase, Bone Specific (BSAP) – bone formation

Prostate: Prostate specific antigen (PSA)

Efficacy: total Testosterone

Pharmacokinetic: Estradiol, Estrone

6.2 Electrocardiogram

The electrocardiogram (ECG) will be a complete, standardized 12-lead recording. ECGs will be evaluated by the Investigator or a qualified designee. Any significant findings, present prior to the first dose of Study Drug (Study Day 1), must be reported on the ECG CRF. Significant findings made after the start of study drug which meet the definition of an AE must be recorded on the Adverse Event CRF.

6.3 Physical Exam

Any significant findings present prior to the first dose of Study Drug (Study Day 1) must be reported on the Physical Exam CRF. Significant findings made after the first dose of Study Drug (Study Day 1) which meet the definition of an AE must be recorded on the Adverse Event CRF. The physical exam (PE₁) will include an assessment of all body systems as well as measurement of height and weight. The exam should include inspection of the thorax for the presence of gynecomastia.

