Although estrogens (administered both acutely and chronically) and GnRH analogs (after continuous chronic administration) suppress testosterone production and testicular function, there are clear differences and advantages for estrogens used for ADT in relation to side effect profile and patient well-being. Estrogens inhibit gonadotropin secretion acting both at the hypothalamic and pituitary level, and by acting on hypothalamic thermoregulatory and vasomotor centers they also eliminate the incidence and magnitude of hot flashes that ensues with the loss of gonadal steroids, both in postmenopausal women and in men undergoing ADT with GnRH analogs. GnRH analogs deplete endogenous sex steroids (e.g., testosterone and estradiol) eliminating both the undesirable (prostate cancer cell stimulation by testosterone) and the beneficial (e.g. bone protective estradiol) effects of the sex steroids. Exogenous estrogens, in addition to suppressing testosterone drive of the tumor, provide a built-in bone sparing activity by decreasing the number and activity of osteoclasts ([Loose and Stancel, 2005](#)) and reducing the incidence and frequency of osteoporosis and bone fractures. Largely due to these side effects, research since the mid-1980s has looked at the use of intermittent ADT as a way to reduce the side effects of continuous androgen suppression with GnRH analogs ([Buchan and Goldberg, 2010](#)). Administration of estradiol at high levels is associated with gynecomastia, a side effect whose impact can be reduced by providing preventive breast radiation. The doses proposed in the present study will result in serum estradiol levels well below those observed in the PATCH study, which may result in a reduction of this bothersome AE. With the use of BHR-200, BHR PHARMA, LLC proposes to provide clinicians with a means to provide continuous androgen suppression to patients who require it, while potentially alleviating the negative side effects associated with ADT.

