3.0 Study Design

Patients will participate in a 24 week double-blind treatment period and will be allowed to continue treatment with their assigned study drug for up to 52 weeks as long as they remain chemically castrated. Entry criteria include prostate cancer patients who are currently receiving treatment with a GnRH agonist depot injection for at least 2 months but not longer than 36 months without interruption, and have testosterone levels < 50 ng/dL at Screening. At the scheduled time point for the next GnRH agonist depot injection, patients will be randomized to receive either placebo or low, mid or high dose BHR-200. The study will enroll 120 patients with 30 patients randomized into each of the 4 treatment groups as shown in Table 1.

Table 1 Treatment group allocation for study BHR-200-201

Treatment Group	Number of Patients	Dose	Number of Pump Actuations*	
Placebo	30	10	0 mg estradiol	1 actuation
		10	0 mg estradiol	2 actuations
		10	0 mg estradiol	3 actuations
BHR-200 Low Dose	30	3 mg estradiol	1 actuation	
BHR-200 Mid Dose	30	6 mg estradiol	2 actuations	
BHR-200 High Dose	30	9 mg estradiol	3 actuations	

*1 actuation of the pump dispenses [REDACTED]

Patients will be offered optional low-dose radiation for the prevention of gynecomastia (Hedlund 2000, Widmark et. al. 2003). Timing of the administration of the low-dose radiation will be at the discretion of the Investigator.

Levels of total Testosterone, estradiol, and estrone will be assessed every 2 weeks for all patients through Week 24 and then every 4 weeks through the End of Study Visit at Week 54 (see [Schedule of Assessments in Appendix 1](#)). Patients will remain in the study and administer daily doses of the assigned study drug until they are no longer chemically castrated as indicated by a measurement of T \geq 50 ng/dL after 4 weeks of double-blind treatment, a rise over baseline PSA of > 0.5 ng/mL is observed, or if 52 weeks of study drug administration have been completed. Patients discontinued from the study will be advised to resume standard of care treatment in consultation with their healthcare provider.

Safety assessments will include AEs as well as the measurement of typical blood chemistry, hematology and urinalysis parameters, as well as coagulation factors, hormone assessments, bone biomarkers, and PSA ([Section 6.1](#)).

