7.0 Study Visits

7.1 Screening

The assessments listed below will be conducted no more than 14 days prior to the first dose of Study Drug (Study Day 1).

- Informed Consent
- Review of inclusion/exclusion criteria
- Demographics: gender, age, race, and, ethnicity
- Review of relevant medical history within past 5 years
- Review of relevant medication/procedure history within past 2 years
- ECG
- Full physical examination including:
 - Height
 - Weight
 - BMI
- Vital Signs: blood pressure, heart rate, respiration rate, and body temperature
- Central laboratory assessments (see [Section 6.1](#) for details):
 - Hematology
 - Blood Chemistry
 - Urinalysis
 - Coagulation Factors
 - Efficacy Assessment

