7.2 Study Day 1 (Week 1): Baseline

The evaluations and assessments listed below will be performed within 2 hours prior to dosing with Study Drug on Day 1. An overnight fast is required for the central

laboratory assessments. It is recommended to collect blood samples in the morning (8-10 AM).

- Reaffirmation of participation
- Affirmation of eligibility criteria
- Review of medical history
- Physical exam, including:
 - Height
 - Weight
 - BMI
- Vital Signs: blood pressure, heart rate, respiration rate, and body temperature
- Record AEs
- Record concomitant medications & procedures
- Central laboratory assessments (see [Section 6.1](#) for details)
 - Hematology
 - Blood Chemistry
 - Urinalysis
 - Coagulation Factors
 - Endocrine Assessment
 - Hormone Assessment
 - Biomarkers: Bone & Prostate
 - Efficacy Assessment
 - Pharmacokinetic Assessment
- Administer Quality of Life Questionnaires:
 - EPIC – Hormonal Component
 - EPIC – Sexual Component
- Randomization
- Dispense study drug
- Study drug compliance –weigh canister(s)
- Record study drug administration
- Issue patient’s study drug administration diary
- *Optional* – Low Dose Radiation for the prevention of gynecomastia*

*Timing is at the discretion of the Investigator.

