7.8 Study Week 12: +84 days (+/- 2 days) from Baseline

The evaluations and assessments listed below will be performed. An overnight fast is required for the central laboratory assessments. It is recommended to collect blood samples in the morning (8-10 AM).

- ECG
- Height, Weight and BMI
- Vital Signs: blood pressure, heart rate, respiration rate, and body temperature
- Record AEs
- Record concomitant medications & procedures
- Central laboratory assessments (see [Section 6.1](#) for details)
 - Hematology
 - Blood Chemistry
 - Urinalysis
 - Coagulation Factors
 - Endocrine Assessment
 - Hormone Assessment
 - Biomarkers: Bone & Prostate
 - Efficacy Assessment
 - Pharmacokinetic Assessment
- Administer Quality of Life Questionnaires:
 - EPIC – Hormonal Component
 - EPIC – Sexual Component
- Dispense study drug
- Study drug compliance –weigh canister(s)
- Collect/issue patient's study drug administration diary

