## 12.4 Physical Examination

Physical examination results will be summarized at each visit as normal, abnormal/clinically significant or abnormal/not clinically significant, and compared in a shift analysis to the baseline result for each physical examination category and in an overall view regardless of post-administration assessment time point. In addition, at each time point, the sums of subjects with normal, abnormal CS, and abnormal NCS values at that time point will be summarized. Also, at each time point the sums of subjects with normal, abnormal CS, and abnormal NCS values at baseline and values at that time point will be summarized.

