## **14 OPTIONAL LOW-DOSE RADIATION**

Patients were offered optional low-dose radiation for the prevention of gynecomastia (Hedlund 2000, Widmark et. al. 2003). Timing of the administration of the low-dose radiation was at the discretion of the Investigator. Data collected on the CRF will be presented in a data listing.

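### Gynecomastia is compared across doses by crude percentage, with one scheduled post-baseline chest inspection at a time that differs by arm and radiation use only listed

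*Protocol*

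**What the plan says.** - **What is examined.** Protocol 6.3 on the physical exam: "The exam should include inspection of the thorax for the presence of gynecomastia".
- **When.** The exam appears at Screening ("Full physical examination including", Protocol 7.1), at Day 1 before dosing ("Physical exam, including", Protocol 7.2), and at Week 54 or End of Study/Early Termination (Protocol 7.22). Week 12 has only "Height, Weight and BMI" (Protocol 7.8), with ECG, and Weeks 24, 36 and 48 are the same. Appendix 1 agrees.
- **What fixes the last exam.** The final visit is 2 weeks (+/- 2 days) after the last dose (synopsis). Treatment ends on T at or above 50 ng/dL from Week 4 onward, on a PSA rise, by choice at Week 24, or at Week 52 (synopsis; Protocol 4.3).
- **How the exam is reported.** SAP 12.4: "Physical examination results will be summarized at each visit", with shifts from baseline and an overall view that ignores time of assessment.
- **Second source.** AEs are collected at every visit, with onset and severity (synopsis; Protocol 9.1) and CTCAE grade (Protocol 9.3). SAP 12.5 tabulates numbers and percentages of subjects.
- **Radiation.** It is offered for prevention and is optional. "Timing of the administration of the low-dose radiation will be at the discretion of the Investigator" (Protocol 3.0). Appendix 1 marks it at Day 1 and Week 24. SAP 14: "Data collected on the CRF will be presented in a data listing".
- **Why it bears on dose.** Protocol 1.0 expects estradiol levels below those of an earlier patch study, "which may result in a reduction of this bothersome AE". Dose selection is the secondary objective.

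**The concern.** Gynecomastia is a known effect of estradiol in men, and the protocol ties it to both dose level and length of exposure. A fair comparison across doses needs similar observation time or an analysis that allows for unequal time. The plan has neither. Men who lose testosterone suppression early leave early and have their one post-baseline inspection then, while men who stay suppressed are treated and observed for longer. If suppression depends on dose, as the sample size assumes, the arms differ in follow-up for a reason linked to treatment.

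Radiation is a second, less certain influence. If given after Day 1 it could differ by arm, and nothing planned shows whether it did. At stake is a tolerability comparison that feeds dose selection, not the primary efficacy result.

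**Working it through.** **1. The plan's own figure.** SAP 4.3 claims at least 90% power with 30 per arm, two-sided Fisher exact test at 5%. Exact enumeration gives 98.2% for 5% versus 50%, and essentially 100% for 5% versus 80% and 5% versus 95%. The claim is met. The response rates are used below only to show how far time on treatment could diverge.

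**2. Schedule against SAP 12.4.** There are three scheduled exams: two before dosing and one after the last dose. None falls on treatment. The by-visit table therefore has one post-baseline entry, and the overall view pools exams made at very different times. Unscheduled exams would not fill the gap, because SAP 7.3 keeps unscheduled data out of analysis except for tables of notable values.

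**3. Mean time of the final exam.** Inputs from SAP 4.3: response r = 5% (placebo), 50% (low), 80% (mid), 95% (high). Assumptions, not in the documents: failures stop at Week F, between 4 and 12, and responders stop at Week R.

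Mean exam week = r × R + (1 − r) × F + 2

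Example, placebo with R = 24 and F = 4: 0.05 × 24 + 0.95 × 4 + 2 = 7.0.

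| Arm | R = 24, F = 4 to 12 | R = 52, F = 4 to 12 |
|---|---|---|
| Placebo | 7.0 to 14.6 | 8.4 to 16.0 |
| Low | 16.0 to 20.0 | 30.0 to 34.0 |
| Mid | 22.0 to 23.6 | 44.4 to 46.0 |
| High | 25.0 to 25.4 | 51.6 to 52.0 |

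If responders stopped at Week 12, the range for placebo is 6.4 to 14.0 and for high dose 13.6 to 14.0. With R = F = 12 all arms are equal at 14.0.

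**4. Effect on crude incidence with no dose effect.** Assume one constant gynecomastia hazard h in all active arms, fixed by an assumed 24-week risk c: h = −ln(1 − c)/24. Let I(t) = 1 − exp(−h × t), with exposure counted to the last dose.

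Crude incidence in an arm = r × I(R) + (1 − r) × I(F)

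High minus low = (0.95 − 0.50) × [I(R) − I(F)] = 0.45 × [I(R) − I(F)]

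Example, c = 40%, R = 24, F = 4: I(24) = 0.400, I(4) = 0.082, so 0.45 × 0.318 = 0.143, or 14.3 points (38.4% high, 24.1% low).

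| 24-week risk c | High minus low, R = 24 | High minus low, R = 52 |
|---|---|---|
| 20% | 4.2 to 7.4 points | 12.5 to 15.6 points |
| 40% | 7.9 to 14.3 points | 20.0 to 26.4 points |
| 60% | 10.5 to 20.6 points | 22.3 to 32.4 points |

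In each cell the smaller value is F = 12 and the larger F = 4. With R = F = 12 the difference is zero.

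**5. Scale at the actual size.** 34/4 = 8.5 men per arm if the split was even (assumed), so one man is 1/8.5, about 12 points.

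**The case against.** **The exam is not the main source.** AEs are collected every 2 weeks to Week 24 and every 4 weeks after that, and exam findings that qualify go on the AE form. A case the patient reports therefore has an onset date and grade whenever the exam falls. This stands: it is wrong to infer that gynecomastia can be found only at the final visit. What a single late inspection risks is missing or late-dating changes the man has not noticed or mentioned. But AE collection also stops sooner in men who stop sooner, and SAP 12.5 makes no allowance for that.

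**Radiation given in response to symptoms.** A reader might infer that it is used this way and so hides gynecomastia at the high dose. The documents do not say so; each statement of purpose is prevention. Discretionary timing and the Week 24 mark permit later use, no more. Symptoms that prompted radiation would normally already be a recorded AE, counted once, and later radiation could not remove it from the incidence. Radiation settled before randomisation would not bias the arms systematically.

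**The two influences oppose each other.** Longer exposure would steepen the apparent gradient, while radiation used more at higher doses would flatten it. The documents do not show which is larger, so no net direction can be claimed.

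**The trial has stopped.** With 34 men, subject-level listings (SAP 7) and an exposure summary by dose group (SAP 12.1), a reader could cross-check AE and radiation dates by hand. That is fair and limits the severity. It does not make the crude percentages comparable.

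**Conclusion.** The point holds as a minor weakness of design and reporting. The schedule has no on-treatment chest inspection, the timing of the only post-baseline one follows a stopping rule expected to differ by arm, and no planned table relates gynecomastia to time on treatment or to radiation. With no true dose effect, unequal follow-up could by itself produce a low-to-high difference of about 4 to 21 points if responders stop at Week 24, or about 13 to 32 points if all reach Week 52.

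These are illustrations. The stop weeks, constant hazard and 24-week risk are assumptions. The stated response rates cover Weeks 4 to 12, so they do not show that 95% of high-dose men stay to Week 24 or beyond. Later failures, PSA stops, withdrawals and the sponsor's early termination would shorten follow-up and may shrink the gap, to nothing in the limiting case shown.

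It would go too far to say that the dose relation is confounded by reactive radiation, or that gynecomastia is a main endpoint: the protocol gives special attention to cardiovascular and thromboembolic events. The text of SAP 5.2 (Safety Endpoints) was not available here, so statements about what the SAP omits apply to its other sections.

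**What to change.** For the data in hand, without new visits:

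1. In SAP 12.5, tabulate gynecomastia AEs by dose group with day of onset, and as a rate per patient-time on treatment or as cumulative incidence by time. This is the step that deals with unequal follow-up.
2. In SAP 14, tabulate radiation by arm with its date relative to first dose. Show gynecomastia with and without radiation given before onset. Do not use an after-onset category as a comparison group, since everyone in it has gynecomastia by definition.
3. Reconcile SAP 12.4 with the schedule by stating that the only scheduled post-baseline exam is at Early Termination/End of Study, and show time on treatment beside it.

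In a running or successor protocol, add thorax inspection to the existing Week 12, 24, 36 and 48 visits. This improves detection on treatment, but men who stop before Week 12 never reach the first added inspection, so step 1 is still needed.

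Cost: one extra descriptive table with small cells at 34 men and, for a future protocol, a brief inspection at visits already planned.
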